## **4 CONCOMITANT MEDICATIONS/MEASURES**

- Patients are allowed to be on concomitant therapy with tamoxifen or aromatase inhibitors for ER+ tumor status.
- Patients may be on concomitant drugs to prevent skeletal related events (SRE), including bisphosphonates and denosumab.
- Study subjects will be allowed to take multivitamins, analgesics (NSAIDS or acetaminophen), antipyretics, and antihistamines for symptomatic relief of local or systemic injection site reactions.
- Patients are allowed to continue on medications as clinically indicated for treatment of chronic medical conditions e.g. hypertension, diabetes, hypercholesterolemia, etc.
- Excluded Therapy:
  - Trastuzumab, pertuzumab, lapatinib, ado-trastuzumab emtansine (TDM1) or other HER2-directed therapies *within 1 week* of study enrollment.
  - Chemotherapy: Concomitant use of chemotherapy is not allowed during this trial.
  - Anti-Cancer Radionuclides: Concomitant use of anti-cancer radionuclides is not allowed during this trial. Patients will be allowed to co-enroll in studies of novel radionuclide imaging agents e.g. Indium CHX-A DTPA trastuzumab.
  - Secondary Hormonal Therapies: Concomitant use of supplementary hormonal treatments other than tamoxifen or aromatase inhibitors is not allowed.
  - Corticosteroids: Concomitant, chronic systemic corticosteroids are not allowed during this trial (excepting emergent use for clinical indications). However, the use

of inhaled corticosteroids, intranasal sprays and topical creams on limited body areas is allowed.

### **Vitamin D3 (Cholecalciferol) Supplementation**

Vitamin D when ingested is metabolized in the liver to 25-OH vitamin D. Inside cells, it is metabolized further by 1-hydroxylase where it is transformed into a seco-steroid hormone that is important to a host of critical cellular and immune functions within the body. Within cells is a second enzyme 24-hydroxylase whose function is to decrease vitamin D, thereby maintaining intracellular vitamin D homeostasis. The classic function of vitamin D is to regulate calcium homeostasis and in turn, bone formation and resorption. However, additional functions of vitamin D have been demonstrated and include effects on immune response by promoting cellular apoptosis and differentiation. The exact role of vitamin D deficiency in prostate, breast, colon and other cancers has been controversial, with some laboratory studies suggesting there is a role and other epidemiological studies suggesting that there is no role or even possibly that supplementation should be avoided. In a recent study by Marshall and colleagues vitamin D supplementation of 4,000 IU per day for one year was examined in men with low risk prostate cancer (Gleason score of 6, 1-6 cores positive out of 12 possible and a PSA <10) under active surveillance. After one year upon re-biopsy, 60% showed a decrease in the number of positive cores, Gleason score or both and in 6% these factors remained unchanged. In addition, PSA levels did not rise. In another study reported by Vieth and colleagues at AACR in April 2012, 66 men scheduled to undergo radical prostatectomy were randomly assigned to receive a daily vitamin D dose of 400, 10,000 or 40,000 IU daily for 3 to 8 weeks prior to surgery. Calcitriol levels in the prostate increased progressively with increasing vitamin D dosing and corresponded with lower levels of Ki67 as well as higher levels of specific growth-inhibitor microRNAs.

Several studies have shown that women with low vitamin D levels have an increased risk of breast cancer incidence and mortality, but research is lacking investigating vitamin D levels and prognostic variables e.g. hormone receptor status, Oncotype DX etc. in this patient population. In a case control study of 194 women s/p breast cancer surgery and 194 cancer-free controls conducted by Peppone and colleagues at the University of Rochester, women with breast cancer were found to have significantly lower 25-OH vitamin levels than controls (32.7ng/mL vs. 37.4 ng/mL respectively, P=0.02).

Importantly, women with suboptimal 25-OH vitamin D levels (<32 ng/mL) had significantly increased odds of having ER-negative (OR = 2.59, 95% confidence interval [95% CI] = 1.08-6.23) and triple-negative cancer (OR = 3.15, 95% CI = 1.05-9.49) than those with optimal 25-OH D concentrations. In addition, women with basal-like phenotype had lower 25-OH vitamin D levels than women luminal A phenotype (24.2 ng/mL vs. 32.8 ng/mL, respectively P = 0.04). In summary, women with a more aggressive breast cancer molecular phenotype (basal-like) and worse prognostic indicators (ER- and triple-negative) had lower mean 25-OH vitamin D levels.

Given its critical role in immune function and possible role in cancer pathophysiology, all patients will have 25-OH vitamin D levels obtained at baseline. Although there is debate about the target level of 25-OH vitamin D for optimum health, most vitamin D experts agree that it should be greater than 40 ng/mL.

- All patients with 25-OH vitamin D levels < 40 ng/mL will be initiated on oral supplements of Vitamin D3 (cholecalciferol) per standard clinical care guidelines. 25-OH vitamin D levels will continue to be monitored at study Weeks 8, 16, 28 and 60.

## **5 BIOSPECIMEN COLLECTION**

### **5.1 CORRELATIVE STUDIES FOR RESEARCH/PHARMACOKINETIC STUDIES**

There are no pharmacokinetic studies that will be performed as part of this clinical investigation.

Evaluation of anti-HER2 antibody and cellular HER2 responses Tetramer and IFN- $\gamma$  ELISPOT Assays will be performed as outlined in [Appendix 6](#). If the patient does not need a confirmatory scan at Week 52, the same set of evaluations will be done at Week 60 instead of Week 52.

Characterization of vaccine-induced antibody profiles (anti-HER2 Antibody Profile) will be performed as outlined in [Appendix 6](#). No additional blood to be drawn: serum will be aliquoted from blood drawn for anti-HER2 antibody studies.

Evaluation of anti-Ad5 antibody immunity will be performed as outlined in [Appendix 7](#).

Characterization of soluble HER2 and anti-HER2 antibodies will be performed on the stored samples as outlined in [Appendix 8](#)**Characterization** of Soluble HER2 and Anti-HER2 Antibodies.

Exploratory correlative studies (Week 0) measuring function-associated mRNAs in whole blood to be performed by [name] and circulating tumor cells (CTCs) and immune subset analysis will be performed by [name] as outlined in [Appendix 9](#).

### **5.2 SAMPLE STORAGE, TRACKING AND DISPOSITION**

#### Collection and storage of Research Samples

For research samples obtained for investigation, the Clinical Support Laboratory, Leidos Biomedical Research, Inc. processes and cryopreserves samples in support of IRB-approved, NCI clinical trials. The laboratory is located in a controlled-access building and laboratory doors are kept locked at all times. Upon specimen receipt each sample is assigned a unique, sequential laboratory accession I.D. number. All products generated by the laboratory that will be stored either in the laboratory freezers or at a central repository facility are identified by this accession I.D. An electronic database is used to store information related to patient samples processed by the laboratory. Vial labels do not contain any personal identifier information. Samples are stored inventoried in locked laboratory freezers and are routinely transferred to the NCI-Frederick repository facilities for long-term storage. These facilities are operated by American Type Culture Collection (ATCC), under subcontract to Leidos Biomedical Research, Inc. Access to stored clinical samples is restricted. Investigators establish sample collections under “Source Codes” and the investigator responsible for the collections, typically the protocol Principal Investigator and/or Lead Associate Investigator, specifies who has access to the collection.

When requests are submitted by the NCI investigator for shipment of samples outside of the NIH it is the policy of the laboratory to request documentation that a Material Transfer Agreement

(MTA) is in place that covers the specimen transfer. The laboratory does not provide patient identifier information as part of the transfer process but may, at the discretion of the NCI investigator, group samples from individual patients when that is critical to the testing process. The NCI investigator responsible for the sample collection is responsible for ensuring appropriate IRB approvals are in place and that an MTA has been executed prior to requesting the laboratory to ship samples outside of the NIH.

Blood, urine and tissue specimens collected in the course of this research project may be banked and used in the future to investigate new scientific questions related to this study. However, this research may only be done if the risks of the new questions were covered in the consent document and the proposed research has undergone prospective IRB review and approval. If new risks are associated with the research (e.g., analysis of germ line genetic mutations.) the Principal Investigator must amend the protocol and obtain informed consent from all research subjects.

Once primary research objectives for the protocol are achieved, intramural researchers can request access to remaining samples provided they have an IRB-approved protocol and patient consent. Access to these samples will only be granted following IRB approval of an additional protocol, granting the rights to use the material.

If at any time, a patient withdraws from the study and does not wish for their existing samples to be utilized, the individual must provide a written request. Following receipt of this request, the samples will be destroyed (or returned to the patient, if so requested), and reported as such to the IRB. The PI will record any loss or unanticipated destruction of samples as a deviation.

Reporting will be per the requirements of Section 0.

#### **5.2.1 Samples collected by the Blood Processing Core of the Clinical Pharmacology Program**

All samples will be bar-coded, with data entered and stored in the Patient Sample Data location. Bar coded samples are stored in bar coded boxes in a locked freezer at either -20 or -80°C according to stability requirements. These freezers are located onsite in the CPP and offsite at NCI Frederick Central Repository Services (ATCC) in Frederick, MD. Samples will be stored until requested by a researcher named on the protocol. All requests are monitored and tracked in the PSDM System. All researchers are required to sign a form stating that the samples are only to be used for research purposes associated with this specific clinical trial (as per the IRB approved protocol) and that any unused samples must be returned to the CPP.

Following completion of this study, samples will remain in storage as detailed above. Access to these samples will only be granted following IRB approval of an additional protocol, granting the rights to use the material. Samples will be stored for future use following completion of the study unless a subject has opted out of the future use of data and specimen.

If, at any time a patient withdraws from the study and does not wish for his/her existing samples to be utilized, the individual must provide a written request. Following receipt of this request, the samples will be destroyed (or returned to the patient, if so requested), and reported as such to the IRB. Any samples lost (in transit or by a researcher) or destroyed due to unknown sample integrity (i.e. broken freezer allows for extensive sample thawing, etc.) will be reported as such to the IRB.

Sample barcodes are linked to patient demographics and limited clinical information. This information will only be provided to investigators listed on this protocol, via registered use of the

PSDMS. It is critical that the sample remains linked to patient information such as race, age, dates of diagnosis and death, and histological information about the tumor, in order to correlate genotype with these variables.

### **5.3 SAMPLES FOR GENETIC/GENOMIC ANALYSIS**

No genetic/genomic analyses will be performed as part of this clinical investigation.

## **6 DATA COLLECTION AND EVALUATION**

### **6.1 DATA COLLECTION**

1. Each patient must meet all eligibility requirements and a completed registration must be sent to the NCI Central Registration Office (CRO).
2. The Consent Document must be signed prior to registration with the CRO.
3. Treatment will be given according to protocol (on-study and treatment notes, reports of adverse events and documentation of any deviation from the study protocol).
4. Data will be entered into a secure software system (C3D Database) produced by OracleTM Corporation (Redwood Shores, CA). Data will be collected based on protocol-specific requirements, verified for accuracy and completeness. Any hard copy data will be kept in locked secure area in the Vaccine Branch Clinical Trials Offices ([name]).
5. Toxicity will be assessed according to the protocol using the CTCAE v4.0 that is available at: [http://ctep.cancer.gov/protocolDevelopment/electronic\\_applications/ctc.htm](http://ctep.cancer.gov/protocolDevelopment/electronic_applications/ctc.htm)
6. Response will be assessed according to the protocol and documentation of response (e.g. CT scans, laboratory reports, dated notes on tumor assessment and clinical assessment as appropriate) using Immune Response Related Criteria as outlined in Section **6.2**.
7. Vaccine report cards associated with each AdHER2 DC vaccination will be obtained for each patient.

The PI will be responsible for overseeing entry of data into an in-house password protected electronic system (C3D) and ensuring data accuracy, consistency and timeliness. The principal investigator, associate investigators/research nurses and/or a contracted data manager will assist with the data management efforts. All data obtained during the conduct of the protocol will be kept in secure network drives or in approved alternative sites that comply with NIH security standards. Primary and final analyzed data will have identifiers so that research data can be attributed to an individual human subject participant.

All adverse events, including clinically significant abnormal findings on laboratory evaluations, regardless of severity, will be followed until return to baseline or stabilization of event.

Document AEs from the first study intervention, Study Week 0, through 30 days after the last study intervention. Beyond 30 days after the last study intervention, only adverse events which are serious and related to the study intervention need to be recorded.

An abnormal laboratory value will be considered an AE if the laboratory abnormality is characterized by any of the following:

- Results in discontinuation from the study
- Is associated with clinical signs or symptoms

- Requires treatment or any other therapeutic intervention
- Is associated with death or another serious adverse event, including hospitalization.
- Is judged by the Investigator to be of significant clinical impact
- If any abnormal laboratory result is considered clinically significant, the investigator will provide details about the action taken with respect to the test drug and about the patient's outcome.

Laboratory and clinical symptom abnormalities less than or equal to Grade 1 will not be graded or assessed for attribution to AdHER2 DC vaccine.

**End of study procedures:** Data will be stored according to HHS, FDA regulations and NIH Intramural Records Retention Schedule as applicable.

**Loss or destruction of data:** Should we become aware that a major breach in our plan to protect subject confidentiality and trial data has occurred, this will be reported expeditiously per requirements in Section [7.2.1](#).

[name] will continue to have access to the data for purposes of data analysis and publication. The necessary data will be sent via encrypted email.

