## **3 STUDY IMPLEMENTATION**

### **3.1 STUDY SCHEMA AND DESIGN**

This is an open label, single site, non-randomized, two-part, phase I study of an autologous dendritic cell (DC) vaccine transduced with AdHER2 to determine vaccine safety, immunogenicity and preliminary activity. The study design schema is outlined in [Figure 11](#).

Once enrollment eligibility is confirmed and informed consent is obtained, the patient will be scheduled for an apheresis of up to 18 liters to collect mononuclear cells by counter-flow elutriation, aliquoted into minimum of 6 vials with up to  $333 \times 10^6$  cells/vial that will be cryopreserved for future preparation of the autologous AdHER2 DC vaccine product. If the collected apheresis products are not adequate for 5 doses of vaccine, the patient may undergo

additional apheresis per investigator's discretion. Co-enrollment in the Indium trastuzumab imaging protocol 07-C-0101 will be offered to those patients that are interested and eligible.

Note: In order to be cleared for the next treatment, a safety visit (i.e., physical and clinical laboratory assessments, review of toxicities/adverse events) must occur within 7 days prior to the treatment. Treatment visits can also be safety visits for previous injections. This is so the treating physician will evaluate the patient for toxicities potentially caused by previous injections.

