***To allow for the possibility of inevaluable patients, an accrual ceiling of 65 will be used.***

### **3.2 DRUG ADMINISTRATION**

All patients will undergo up to 18-liter apheresis to remove peripheral blood monocytes for dendritic cell preparation. Cells used for subsequent dendritic cell maturation will be derived from monocytes frozen during the initial apheresis. Autologous AdHER2 dendritic cell vaccine will be manufactured under cGMP conditions by the NIH Clinical Center Department of Transfusion Medicine as outlined in [Appendix 3](#). If the mononuclear cells or plasma collected are not adequate for minimum of 5 doses of vaccine, the patient will undergo optional additional leukapheresis or plasma collection per investigator's discretion.

- Autologous AdHER2 DC vaccine preparations will be assessed for release standards (nucleated cell content and concentration, appearance, flow cytometric verification of DC validation markers, viability  $\geq 60\%$ , and product sterility and safety testing) as well as for HER2 expression (percent of cells expressing HER2/neu and the ratio of geometric mean fluorescent intensity (MFI) of HER2/neu expression to isotype control).
- For patients in both Part I and Part II of the study, autologous AdHER2 DC vaccinations will be dosed according to enrollment dose levels (5, 10, 20, or  $40 \times 10^6$  viable cells/vaccine) and administered intradermally in up to two injection sites at Weeks 0, 4, 8, 16 and 24 for a total of five vaccinations. Vaccine will be administered in the 3SE Day Hospital and patients will be monitored for immediate adverse event vaccine reactions (VS, clinical assessment) for 1 hour following their first HER2 DC vaccine dose. If no adverse reactions are observed with the first vaccination, patients will be monitored for 15 minutes for all subsequent vaccinations.
- If an adverse reaction is observed following the first vaccine, the reaction will be characterized and a determination made as to whether it is considered a dose limiting toxicity (DLT) as outlined in Section [3.1.1](#). If the adverse reaction is determined not to be a DLT, the duration of post-vaccination monitoring for subsequent vaccinations will be determined by the Principal Investigator and Lead Associate Investigator as clinically indicated depending on the severity of the initial vaccine reaction.

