## **8.2 ASSESSMENT OF SAFETY EVENTS**

AE information collected will include event description, date of onset, assessment of severity and relationship to study product and alternate etiology (if not related to study product), date of resolution of the event, seriousness and outcome. The assessment of severity and relationship to the study product will be done only by those with the training and authority to make a diagnosis and listed on the Form FDA 1572 as the site principal investigator or sub-investigator. AEs occurring during the collection and reporting period will be documented appropriately regardless of relationship. AEs will be followed through resolution.

SAEs will be:

- Assessed for severity and relationship to study product and alternate etiology (if not related to study product) by a licensed study physician listed on the Form FDA 1572 as the site principal investigator or sub-investigator.
- Recorded on the appropriate SAE report form, the medical record and captured in the clinical database.
- Followed through resolution by a licensed study physician listed on the Form FDA 1572 as the site principal investigator or sub-investigator.

For timeframe of recording adverse events, please refer to Section **6.1**.

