#### **Autologous Cell Harvest**

Blood collection will be by standard apheresis: up to 18L of whole blood will be processed in order to collect peripheral blood mononuclear cells (MNC) with a target yield of at least  $2.2 \times 10^9$  monocytes. Lymphocytes will also be cryopreserved for immunologic assays. Apheresis will be performed in the Clinical Center (CC) Department of Transfusion Medicine (DTM) using approved standard operating procedures. Bilateral peripheral venous access or a venous dual lumen catheter will be used for apheresis. Prophylactic intravenous CaCl2 and MgSO4 infusions may be administered during apheresis to treat or prevent citrate toxicity at the discretion of the DTM physician per routine. Autologous monocytes for dendritic cell culture will be enriched from peripheral blood MNC apheresis collections by counter-flow elutriation, aliquoted into multiple vials and cryopreserved for future preparation of the dendritic cell products: target of at least 6 vials with  $\sim 333 \times 10^6$  cells/vial. Additional apheresis will be offered per investigator's discretion if the collected cells or plasma are not sufficient to manufacture at least 5 vaccine doses. All cell processing will be conducted in accordance with approved DTM policies and procedures.

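### AE recording opens at Study Week 0, after the initial apheresis, so non-fatal complications of that procedure need not enter the trial's AE data

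*Combined protocol and SAP*

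**What the plan says.** Section 6.1 (Data Collection) defines when adverse events are collected: "Document AEs from the first study intervention, Study Week 0, through 30 days after the last study intervention". After the window closes, it still asks for events that are both serious and related. It makes no matching provision for the time before the window opens.

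Section 8.2 (Assessment of Safety Events) sets no window of its own: "For timeframe of recording adverse events, please refer to Section" 6.1. Its duty to document is limited to that window: "AEs occurring during the collection and reporting period will be documented appropriately regardless of relationship".

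On the procedure itself, Section 3.1 says that once eligibility is confirmed and consent obtained, "the patient will be scheduled for an apheresis of up to 18 liters to collect mononuclear cells by counter-flow elutriation". Section 3.2 applies this to all patients and explains its purpose: "Cells used for subsequent dendritic cell maturation will be derived from monocytes frozen during the initial apheresis". Appendix 3 (Autologous Cell Harvest) describes the access, "Bilateral peripheral venous access or a venous dual lumen catheter will be used for apheresis", and foresees a complication: calcium and magnesium "infusions may be administered during apheresis to treat or prevent citrate toxicity".

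In the study calendar (Section 3.4), apheresis sits in the screening column of the vaccine row. The adverse-event row is empty in that column and first ticked at Week 0.

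**The concern.** Section 6.1 gives one start date under two names, and the names point to different days. The first thing done to a participant purely for the study is the apheresis, but the rule and the calendar both start the clock at the first vaccine dose. Whatever happens at the apheresis, or between it and Week 0, lies outside the period in which events must be documented.

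The product is autologous, so no one can receive it without the harvest. Section 12.2 describes the trial as first in human, and the first primary objective is the safety and toxicity of this vaccination. If the harvest is left out, the general toxicity report describes less than participants undergo. The patients most likely to drop out of view are those who had apheresis and then received no vaccine.

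**Working it through.** No sample size, power or error rate is involved, and the plan states no figure to reproduce. The check is on the order of events and on which rule covers each step.

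1. **Order.** Consent, then the initial apheresis (Section 3.1; screening column of the calendar), then manufacture from the frozen monocytes (Section 3.2), then the first vaccine at Week 0. The dose is made from the harvested cells, so the initial apheresis must precede Week 0.

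2. **Window.** Section 6.1 opens it at Week 0. The calendar row agrees. Section 8.2 defers to 6.1. Section 8.3 sets a 24-hour deadline for serious events but no start date, so the only stated timeframe for those is also the one in 6.1.

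3. **Initial apheresis against window.** Step 1 places it before the opening in step 2 for every patient.

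4. **Repeat apheresis.** Sections 3.1 and 3.2 and Appendix 3 allow another collection if the material does not suffice for five doses, and do not confine it to the time before Week 0. A repeat after Week 0 is inside the window; a repeat before it is not.

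5. **Patients never vaccinated.** Section 3.5.3.6 removes patients who progress rapidly or deteriorate between screening and baseline. The product must also meet a release viability of at least 60% (Section 3.2), and Section 1.2.6 reports donor-dependent viability and one healthy donor with very poor yield. The documents do not say how many patients would have apheresis and then no vaccine. Any who do never reach Week 0, so their window never opens.

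6. **Other reporting routes.** Section 7.3 sends deaths within 30 days of a research intervention to the Clinical Director, unless due to progressive disease. Section 7.2.1 sends unanticipated problems to the IRB. Section 7.4.2.1 asks for a count of dropouts with brief reasons. The expedited reports in Section 7.4.1 concern events associated with use of the vaccine. None of these requires an entry in the trial's AE data, and a non-fatal, foreseeable event such as a citrate reaction could trigger none of them.

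7. **Extent.** Planned evaluable patients: 30 + 30 = 60, with an accrual ceiling of 65. All of them have an initial apheresis, so the gap applies to up to 65 procedures. The documents give no complication rate. As an assumption only, with a per-patient rate of 1% to 3%, the chance of at least one event in 60 patients is 1 − 0.99^60 = 0.45 to 1 − 0.97^60 = 0.84, with 60 × 0.01 = 0.6 to 60 × 0.03 = 1.8 events expected. The conclusion does not depend on this range.

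**The case against.** The strongest reply is that the window follows the plan's own definitions. Section 8.1.1 defines an adverse event in a subject given a pharmaceutical product, and Section 8.1.5 attributes events to the study product. Before Week 0 no product has been given, so starting at first exposure is coherent. This has weight, but Section 6.1 names the first study intervention as the start, and the apheresis is one. If apheresis was meant to count, the sentence conflicts with its own date and with the calendar. If it was not, the report leaves out a mandatory step. Either way the text needs changing.

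Several stronger conclusions are tempting, and the documents do not support them:

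- **That the primary cardiac result is biased.** Cardiac dysfunction is measured by change in LVEF, the dose-limiting toxicities concern vaccine-period events, and the stopping rules count cardiac toxicity and vaccine-attributed deaths. None of these changes.
- **That apheresis harm can never appear, or that the recorded count is zero whatever the true rate.** A repeat after Week 0 is captured, and deaths and unanticipated problems have other routes. Patients are also examined, with laboratory tests, in the 7 days before a dose, so an unresolved complication might be noticed then.
- **That the study places catheters.** Appendix 3 says only that peripheral access or a dual lumen catheter is used, and Section 2.2.1.4 excludes patients with inadequate access. Placement for the study is an inference.
- **That the apheresis risk is undisclosed.** Section 12.4 does not discuss it, but the consent pages and the apheresis procedures are not among the material reviewed.

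In addition, Section 6.1 leaves abnormalities of Grade 1 or below ungraded and unattributed, so mild symptoms would add little even inside the window.

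**Conclusion.** The point holds in a limited form. As written, non-fatal complications of the initial apheresis need not enter the AE data, and patients who have apheresis without vaccination have no AE window. This follows from Sections 6.1 and 8.2 and the calendar read together, and no other section reviewed brings the events back in. It assumes that the start of the window is Week 0, as Section 6.1 states and the calendar confirms.

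The gap affects one procedure in every patient. The number of events lost is unknown, and the 1% to 3% range is only for scale. What is incomplete is the general safety and toxicity report. It should be corrected because the change is cheap and the trial is first in human, but it does not threaten the trial's main safety decisions.

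**What to change.** - In Section 6.1, open the window with: 'Document AEs from the start of the first study-specific procedure (apheresis, including any venous access placed for it)'. Keep the existing 30-day end. For a patient never vaccinated, the last intervention is then the apheresis, so that patient's window both opens and closes.
- In the Section 3.4 calendar, tick the adverse-event row at apheresis.
- In the analysis, tabulate pre-vaccine procedure-related events separately from vaccine-related events, with all patients who started apheresis as the denominator. Section 8.2 already collects an alternate cause for events not related to the product, and that field can identify the apheresis.

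The cost is one sentence, one calendar tick, one table and a few extra AE entries. No dose, clinical rule, sample size or stopping boundary changes.
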